1.4.2. Exclusion Criteria

- 1.4.2.1. The patient cannot be undergoing chemotherapy at the time of enrollment unless it is post-transplant maintenance chemotherapy. Patients undergoing post-transplant maintenance chemotherapy are permitted to enroll.
- 1.4.2.2. The patient must have no evidence of disease progression or recurrence. Specifically, for the prostate cancer population, the patient must have no evidence of disease progression on their current ADT regimen at the time of enrollment.
- 1.4.2.3. The patient must not be a night shift worker, where night shift is defined as working a significant number of hours (i.e. more than half) between the hours of 11PM and 6AM on a regular basis.

1.5. *Intervention Plan*

- 1.5.1. Participants will be consented, enrolled, and randomized remotely with a Research Coordinator prior to beginning the trial. A review of inclusion/exclusion criteria will be conducted to determine the patient's eligibility for enrollment. Study procedures will be reviewed with the patient, and documentation of informed consent will be obtained. After signing the informed consent form (ICF) either in person or electronically using SignNow or other process approved by the University of Michigan IRBMED, patients will be assigned a unique study ID number in sequential order. Those who are found to be ineligible will be replaced.
- 1.5.2. After providing informed consent, the participant will be provided, in the clinic or via mail, a wearable device and a pair of glasses, which will be either blue-blocking (intervention group) or clear (control group). Both of these are described in detail in **Appendix A**. When both are in the participant's possession, the study coordinator will schedule a second meeting with the participant to onboard them to the specifics of the study.

- 1.5.3. The study coordinator will walk the participant through setting up the app and entering their Research ID number. They will ensure that the participant is able to connect to the wearable device via their phone and will explain to the subject that they should not wear the blue-blocking glasses while driving or if their vision will be impaired by them in a way that challenges their mobility.

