- 4.4. *Post-Intervention Evaluation*: PROMIS Patient-Reported Outcomes (PROs) – Well-being or HRQOL assessments will be completed at 12 weeks, post-intervention. This survey must be completed within two weeks after the 12-week intervention period. The surveys will be obtained directly through the SYNC app on mobile phones. Based on prior work, our Study Team has experience administering PROMIS PROs on mobile devices.
- 4.5. *Participant Withdrawal*: At any time, a participant may request that her or his data no longer be collected. The participant may make this request to the Research Coordinator or to any member of the Study Team. A note will be made in the patient chart documenting the reason the patient withdrew from the study. Participants may also be removed for the following reasons: development of disease recurrence or progression, in the event that the IRB or sponsor decides to close the study, or if the treating physician thinks it is no longer in the best interest of the patient.
- 4.6. *Study Regulations*: The trial will be performed in accordance with all applicable regulatory requirements and laws.
- 4.7. *Risks*.

4.7.1. Wearable Sensor Device: Patient Subjects who agree to wear the device(s) for data collection may experience mild skin irritation, which will be monitored by the care team. The subject can decline to wear the device(s) or request to try a different device(s) that may be more comfortable. Subjects who decline to wear the wearable device will be replaced and not included in the statistical analysis. All subjects will be instructed to remove the device before any scans or radiation therapy.

4.7.2. Confidentiality: There is a possible risk of loss of confidentiality. However, every effort will be made to keep your medical information confidential. We will code data by assigning a number to each individual patient and then store the data by that number. No mention of patient subject identities is made in analyses of the data or in any publications, which result from such research.

4.8. **Adverse Event Reporting Requirements.**

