5. STATISTICAL CONSIDERATIONS

- 5.1. *Study Design.* The clinical trial is a two-arm randomized controlled trial. After completion of the intervention, data analysis will be conducted according to the statistical analysis plan outlined below. Descriptive statistics will be performed prior to conducting the statistical analyses. An intention-to-treat (ITT) analysis of the results will be based on the initial assignment of the randomized participants. With the ITT approach, participants will be analyzed according to the treatment assignment, even if the participant drops out of the study. The ITT approach minimizes biased comparisons among the treatment arms. Missing data will be imputed using the last collected data from the subject prior to dropout.
- 5.2. *Accrual.* It is estimated that 18-months will be necessary to enroll the targeted sample size. Accrual will be reported by race, ethnicity, gender, and age.
- 5.3. *Study Duration.* Survey results and wearable data will be actively collected from participants over the course of 12 weeks. At the conclusion of the 12 weeks, passive collection of wearable data through the app will continue for up to one year for each participant who opts-in to continue using the app. Medical records may be accessed for up to five years after the conclusion of the 12-week collection period.
- 5.4. *Randomization.* Blocked randomization will be used to limit bias and achieve an equal distribution of participants to the intervention and control arms of the study (69 randomized, 69; with 23 from each cancer population in each arm). This approach will recruit participants in small blocks to ensure that half of the participants within each block will be allocated to the treatment and the other half to the control. The size of the blocks will be permuted to limit selection bias, and within each block, the order of patients will be random. The study statistician will create a randomization list before the study begins enrollment using the statistical package R. This list will be used by the study group in assigning patients to the correct study arm.
- 5.5. *Blinding.* Study arm assignments cannot be blinded to the investigators or the rest of the study team because it will be known whether participants have SYNC on their mobile device or not (due to technical purposes).

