5.12. *Analysis of Primary Endpoint.* Analysis will be an intent-to-treat analysis that includes all participants. Mean Global Health scores at the end of the trial will be compared using a two-sample *t*-test (or Wilcoxon Rank Sum test if non-normality is apparent) with a significance level of 0.05. Linear regression models will be performed to complement the results of the *t*-test and adjust for specific baseline participant's characteristics (e.g., demographic, social, environmental) to increase the precision of our inference. There is a possibility that patient characteristics will be unbalanced since our randomization scheme will be applied to participants. Thus, our models also will assess potential moderating or mediating effects.

5.13. *Analysis of Secondary Endpoint.*

Mean PROMIS scores (PROMIS sleep disturbances, anxiety, depression, physical function, and global health) for each arm at the end of the trial will be compared using a two-sample *t*-test (or Wilcoxon Rank Sum test if non-normality is apparent) with a significance level of 0.05. Linear regression models will be performed to complement the results of the *t*-test and adjust for specific baseline participant's characteristics (e.g., demographic, social, environmental) to increase the precision of our inference. There is a possibility that patient characteristics will be unbalanced since our randomization scheme will be applied to participants. Thus, our models also will assess potential moderating or mediating effects.

5.14. *Analysis of Exploratory Endpoints.*

5.14.1. Patient activity. The accelerometer data of each subject will be transformed into a low-dimensional representation using motif discovery algorithms.⁷⁹ Such techniques are completely data-driven, and search for motifs (i.e., patterns) in the data that occur more often than chance. A signal can then be represented by the number of times a particular motif occurs. Others have successfully used such techniques for representing a variety of waveform data, including accelerometer and continuous glucose data.⁸⁰⁻⁸² The accelerometer data will be processed to derive estimates of total sleep duration (i.e., hours per night), wake after sleep onset, and sleep efficiency (i.e., ratio of sleep to wake). The variables will be compared between arms.

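### Section 4.7.1 replaces and excludes participants who decline the wearable, without limiting this to refusals before randomisation, and so contradicts the analysis set in 5.1, 5.11.1 and 5.12

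*Combined protocol and SAP*

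**What the plan says.** Two parts of the combined protocol and SAP decide who is analysed.

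- **Section 4.7.1 (Risks, wearable sensor device).** After a sentence on skin irritation, it says: "The subject can decline to wear the device(s) or request to try a different device(s) that may be more comfortable". The next sentence is the rule: "Subjects who decline to wear the wearable device will be replaced and not included in the statistical analysis".
- **Section 5.1.** The analysis is intention-to-treat on initial assignment, and "participants will be analyzed according to the treatment assignment, even if the participant drops out of the study".
- **Section 5.12.** On the primary endpoint: "Analysis will be an intent-to-treat analysis that includes all participants".
- **Section 5.11.1.** The primary analysis population is everyone enrolled and consented who completed the baseline outcome measures. Wearing the device is not a condition.

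The order of events is given under Study Design. In 1.5.1, "Participants will be consented, enrolled, and randomized remotely with a Research Coordinator prior to beginning the trial". In 1.5.2, after consent, the participant is supplied with "a wearable device and a pair of glasses, which will be either blue-blocking (intervention group) or clear (control group". In 1.5.5, baseline assessments follow randomisation.

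**The concern.** An intention-to-treat comparison keeps everyone who was randomised in the arm to which they were assigned. A rule that takes people out because of what they do after assignment, and fills their places with others, gives up that protection. Replacement restores the head count but not the randomised comparison.

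The plan does not say which section prevails. An analyst who follows section 5 keeps a randomised decliner who has baseline data; an analyst who follows 4.7.1 drops the same person. The primary test could then be run on different people, and the choice could be made after outcomes are known. Section 5.5 adds that the study team cannot be blinded, so whoever decides that a participant has declined will know the arm.

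**Working it through.** **1. Can the rule reach randomised participants?** The device is shipped or handed over with glasses that already differ by arm, so assignment precedes receipt. The sentence before the rule places declining next to irritation from wear, which can only happen after receipt. No eligibility criterion in 1.4.1 or 1.4.2 requires willingness to wear the device, so nothing screens refusers out beforehand. The only other replacement rule, in 1.5.1, covers people found ineligible. The list of reasons for removal in 4.5 does not include refusing the device.

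**2. Where does one such person fall?** Take a randomised participant who completes baseline, then declines the device but answers the surveys.

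- 5.1: in, as assigned.
- 5.11.1: in, because baseline is complete.
- 5.12: in.
- 4.7.1: out, and replaced.

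**3. Is the outcome lost when the device is declined?** Sections 1.5.5, 4.3 and 4.4 deliver the surveys through the app, and no section makes them depend on the device. Exclusion can therefore discard observed fatigue scores.

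**4. Is declining defined?** No. Section 1.5.5 asks for continuous wear over twelve weeks, while Appendix A leaves the frequency of Fitbit wear to the subject. These two statements must be reconciled, and no threshold separates partial wear from declining.

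**5. The plan's own numbers.** Inputs from 5.7: effect 0.5 SD, two-sided 0.05, power 0.80, dropout 7%.

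- Normal approximation: n per arm = 2(1.96 + 0.8416)² / 0.5² = 62.8, so 63.
- Two-sample *t*-test: 63.77, so 64 per arm, with power 0.801.
- Dropout: 64 / 0.93 = 68.8, so 69 per arm and 138 in total.

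The stated figures reproduce. None depends on the wearable rule.

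**6. Size of any bias.** Let p be the share of an arm excluded and δ the mean difference, decliners minus wearers. Excluding them moves that arm's mean by −pδ, so the bias (intervention minus control) is p_C δ_C − p_I δ_I. It is zero if p and δ are the same in both arms. The documents give none of these quantities, so the following only shows the scale:

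- One extra exclusion from an arm of 69, with δ assumed at 0.5 to 1.0 SD: 0.5/69 = 0.007 to 1.0/69 = 0.014 SD, or 0.07 to 0.14 T-score points at SD 10.
- Assumed 5% excluded in one arm and 10% to 15% in the other, same δ range: from (0.10 − 0.05) × 0.5 = 0.025 SD to (0.15 − 0.05) × 1.0 = 0.10 SD, in either direction. Two-sided type I error at 64 per arm would be 0.052 to 0.087.
- This is not a bound. Equal 10% exclusions with δ of +0.5 and −0.5 SD also give 0.05 + 0.05 = 0.10 SD.

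The only wear evidence is the usability work in Background 1.6 and 1.8. Taking these as the same eight-person study and assuming that nobody declined, the exact 95% upper limit is 1 − 0.025^(1/8) = 0.369. That neither supports nor excludes the rates above.

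**7. Possible power cost of keeping decliners.** If 0.5 SD were the effect in wearers only, and a share q of the intervention arm declined and gained nothing (both assumed), the effect becomes 0.5(1 − q):

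| q | Power, 64 per arm | Power, 69 per arm |
|---|---|---|
| 0 | 0.801 | 0.830 |
| 5% | 0.760 | 0.791 |
| 10% | 0.714 | 0.747 |
| 15% | 0.665 | 0.698 |

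**The case against.** The best defence is that declining means refusing at consent. Section 4.7.1 sits under risks and opens with "Patient Subjects who agree to wear the device(s) for data collection may experience mild skin irritation", so declining may be simply the opposite of agreeing. Procedures are reviewed before consent is documented (1.5.1), and assignment follows eligibility and consent (4.2). On that reading nobody randomised is removed. This is a possible reading and may be what was meant, but 4.7.1 does not say so, and its sentence on irritation and alternative devices points to refusal after wear.

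A second defence is that an analyst would work from 5.11.1, which has no wearable condition. That makes section 5 the likelier choice in practice. But 4.7.1 speaks expressly about the statistical analysis, and no section gives precedence.

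A third is that the rule has a rationale. Appendix B says the recommendations are calculated from wearable data, so a decliner may not receive the assigned recommendations. This is a fair reason to want wearers. It describes non-adherence, however, which intention-to-treat keeps in the comparison.

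A reader might go further and infer that the rule biases the trial, perhaps towards the intervention. The documents do not support that: a wearable is given in both arms, early users reported no difficulty wearing it (Background 1.6), and no decline rate or imbalance is given. Nor do they support a claim that the sample size is wrong. Section 5.7 states its effect as a difference between the arms, not among wearers.

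**Conclusion.** The contradiction stands. As written, 4.7.1 can remove and replace randomised participants whom 5.1, 5.11.1 and 5.12 keep, so the primary analysis set is not uniquely defined. This rests on the wording and the stated order of events alone. It needs no assumption about how many decline, and it should be settled before data are locked.

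The size and direction of any resulting bias cannot be obtained from the documents and may be zero; the figures in steps 6 and 7 are illustrations under assumed rates. If refusal at consent was the intention, the plan needs only to say so.

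There is a smaller related point. Because baseline is collected after randomisation, the baseline condition in 5.11.1 already narrows the promise in 5.12 to a mild modified intention-to-treat set.

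**What to change.** 1. In 4.7.1, limit replacement and exclusion to refusals before randomisation, and confirm willingness to wear the device before the arm is assigned.
2. Keep randomised decliners in survey follow-up and in the primary analysis as assigned, unless they withdraw under 4.5 ("At any time, a participant may request that her or his data no longer be collected"). Align 4.7.1 with 5.1, 5.11.1 and 5.12.
3. Report the number of decliners by arm. Make any wearers-only analysis a sensitivity analysis.
4. In 5.11.1, either drop the baseline condition or label the set modified intention-to-treat, and report missing baseline by arm. If the condition is dropped, say how participants with no score are handled, because the last-value rule in 5.1 has nothing to carry forward for them.

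The cost is a few sentences and one question before randomisation. No sample-size figure changes: 64, 69 and 138 stand for a 0.5 SD difference among all randomised. The real downside is dilution if randomised decliners gain nothing, which the question before randomisation should reduce.

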Eligibility Criteria: All patients will be outpatient, though most will still be undergoing long-term treatment: breast cancer patients often receive endocrine therapy; prostate cancer patients often receive androgen deprivation therapy; and HSCT patients will be recovering their immune system from the high-dose chemotherapy that was administered in preparation for their transplant. We will exclude patients actively receiving chemotherapy at the time of enrollment to avoid potential confounding factors. However, post-transplant maintenance chemotherapy will be allowed. We will also exclude night shift workers, where night shift work is defined as working a significant number of hours (i.e. more than half) between the hours of 11PM and 6AM on a regular basis. Participants will be required to be able to read and write English, be at least 18 years old, and report their baseline fatigue level as

moderate (4 or higher on a 10-point scale). Patients must own an iPhone 6s or later (with iOS 14 or later, or willing to update to iOS 14+) and be able to complete surveys on it, or they must agree to utilize a loaner iPhone provided by the study team to use during the study and return at the end of the study.

Treatment Description: All participants will be given access to an app into which they enter their research ID number. The research ID number will determine which version of the app is loaded on their phone. Participants will also be given a wearable device and a pair of glasses. Interventional group participants will be given a pair of blue light-blocking glasses. Participants in the control group will be given a pair of glasses that does not block visible light. All participants will wear the wearable device day and night over the course of the 12-week trial. Participants in the interventional group will use a version of the app that gives them personalized lighting recommendations (e.g. "Seek bright light") and a time interval over which the recommendation applies (e.g. "8:30 - 9:45 am").

Control arm: Control group participants will use a version of the app that makes recommendations to use the glasses; however, the time intervals recommended will be chosen to occur in the period of time when any change in lighting is expected to have no effect on the circadian clock (e.g. around noon, for many people already entrained to a diurnal schedule). Participants will be informed that they should only wear the glasses if it is reasonable for them to do so.

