- 1.5.8. Light-blocking and “dummy” glasses: Participants will be provided either blue-blocking glasses (intervention group) or clear glasses that do not block visible light (control). The blue-blocking glasses are meant to reduce the circadian effect of light at certain times for participants. Both pairs of glasses will be capable of being worn over regular glasses for vision impairment. Participants will be informed not to wear the glasses while driving, or when doing motor activity that risks injury with vision impairment. They will also be informed that they are not required to wear the glasses if doing so makes them feel uncomfortable; e.g. if they are out in public.
- 1.5.9. Wearable sensor device: Each participant will be given a wearable sensor to wear throughout the treatment period, except while in water or when charging. The goal is to collect objective, continuous, multi-parameter physiological data (e.g., total

hours of sleep, sleep quality, total number of steps) on patients throughout the treatment period to correlate with their subjective, snapshot participant-reported outcomes collected over the course of the trial. The de-identified wearable data will be stored on servers purchased by the small business partner, Arcascope. For troubleshooting, detailed instructions will be provided for all participants, and customer support will be available 8AM – 5PM CST. Our team is available by pager after hours, if needed.

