Adverse events related to this intervention are not expected, as the focus of this intervention (if randomized to the intervention group) is on lighting and minimal-risk behavioral interventions. However, any adverse events resulting from research procedures will be reported to IRBMED per institutional guidelines. In the event an AE does occur, the PI will determine the attribution/relatedness of each AE. Expected side effects from anti-hormonal therapies, anti-HER2 therapy, GVHD will not be reported for this trial.

4.9. ***Participant Data Security and Compliance***. All identifiable information about the patient will be stored on a secure, password-protected core image laptop computer in [name] [name]'s Laboratory (MPB) following rules for secure data storage (e.g., M+Box or Dropbox). Research devices will not interface with MiChart. All study personnel will be HIPAA and PEERRS certified. All study information will be stored in password-protected encrypted files and identified by case number. The technologies proposed in this proposal have all been carefully reviewed, and approved by the governing bodies at Michigan Medicine. All regulatory and security requirements have been met and have been fully documented in accordance with the policies and best practices that govern the use of technology for patient care and research at Michigan Medicine. The MiChart web services were built and are supported by HITS, and their use for this project has been approved by HITS. All standard procedures and protocols for security and data integrity that apply to this project are being followed. All PHI will be stored in the HITS Oracle Database.

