4.10. ***Data Safety Monitoring Plan***. This study will be monitored in accordance with the NCI approved University of Michigan Rogel Cancer Center Data and Safety Monitoring Plan. The study team will meet every six months or more frequently depending on the activity of the protocol. The discussion will include matters related to the safety of study participants (SAE/UaP reporting), validity and integrity of the data, enrollment rate relative to expectations, characteristics of participants, retention of participants, adherence to the protocol (potential or real protocol deviations) and data completeness. At these regular meetings, the protocol specific Data and Safety Monitoring Report form will be completed and signed by the Principal Investigator or by one of the co-investigators. Data and Safety Monitoring Reports will be submitted to the University of Michigan Rogel Cancer Center Data and Safety Monitoring Committee (DSMC) every six months for independent review.

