1. Reliability: The degree to which a measure is free of error. It can be estimated by the internal consistency of the responses to the measure, or by correlating total scores on the measure from two time points when there has been no true change in what is being measured (for z-scores, reliability = $1 - SE^2$).
2. Precision: The consistency of the estimated score (reciprocal of error variance).
3. Information: The precision of an item or multiple items at different levels of the underlying continuum (for z-scores, information = $1/SE^2$).
4. Standard Error (SE): The possible range of the actual final score based upon the scaled T-score. For example, with a T-score of 52 and a SE of 2, the 95% confidence interval around the actual final score ranges from 48.1 to 55.9 ($T\text{-score} \pm (1.96 \times SE) = 52 \pm (1.96 \times 2) = 48.1 \text{ to } 55.9$)

The final score is represented by the T-score, a standardized score with a mean of 50 and a standard deviation of 10 points.

5.9. *Interim Analysis*. There will be no interim analyses for efficacy or futility for this trial.

5.10. *Patient Characteristics*. Patient characteristics will be summarized for all participants. Patient characteristics to be examined may include: age, gender, race/ethnicity, treatment and pathology information (including dates), and clinical outcomes; e.g. survival, relapse, and toxicities.

5.11. *Analysis Populations and General Analysis Guidelines*.

5.11.1. Primary Analysis Population. All participants enrolled, consented, and completing at least the baseline outcome measures will be included in the primary analysis population. Analyses for the primary and secondary endpoints will use the primary analysis population: The primary analysis will occur once all patients have been followed for the duration of the 12-week trial, data adjudication completed, and data are locked.

5.11.2. General Analysis Guidelines. Primary analyses for the primary, secondary, and exploratory endpoints will use the primary analysis population. Analyses of each endpoint in each population will follow the

analysis plans, as described below. We expect minimal missing data (<5%) for the primary endpoint and secondary endpoints based on past experience with mobile app studies.

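### Section 4.8 excludes expected background-treatment effects from reporting, so a SYNC-arm excess of non-serious events of this kind has no stated by-arm tabulation and no stated route to the DSMC

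*Combined protocol and SAP*

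**What the plan says.** Section 4.8 (Adverse Event Reporting Requirements) makes three statements that matter here.

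- On what goes to the IRB: "any adverse events resulting from research procedures will be reported to IRBMED per institutional guidelines".
- On who judges cause: "In the event an AE does occur, the PI will determine the attribution/relatedness of each AE".
- On what is left out: "Expected side effects from anti-hormonal therapies, anti-HER2 therapy, GVHD will not be reported for this trial".

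Section 5.5 (Blinding) adds: "Study arm assignments cannot be blinded to the investigators or the rest of the study team".

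Section 4.10 (Data Safety Monitoring Plan) describes a second channel. The study team meets at least every six months, and on content it says: "The discussion will include matters related to the safety of study participants (SAE/UaP reporting". A report form signed by the principal investigator or a co-investigator then goes to the DSMC every six months for independent review. The exclusion in 4.8 is not repeated there, and no by-arm content is specified.

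In the statistical section, 5.10 (Patient Characteristics) allows a summary covering all participants of items that may include "clinical outcomes; e.g. survival, relapse, and toxicities". It does not say that the summary is by arm. Section 5 contains no other adverse event analysis.

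**The concern.** Randomization lets a trial separate harm caused by the intervention from background toxicity: count the events in each arm, whatever anyone thinks caused them, and compare. A rule that removes events by presumed cause acts before that comparison. Here the presumption is made by one person who knows the arm, without a list of expected events to constrain the judgment and without an exception for an increase in frequency or severity.

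The arms differ in ways that could plausibly shift non-serious events. Under Appendix B, only the full app advises on sleep timing, exercise timing, caffeine avoidance and going outdoors. Appendix A gives the SYNC arm orange blue-blocking lenses and the control arm clear ones. If an event already familiar under hormone therapy became more common with SYNC, each case could reasonably be classed as expected and the excess would go uncounted. Events that were never logged cannot be tabulated later.

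**Working it through.** The plan gives no figure on this point, so the check is mainly a reading of the passages side by side, with one count and one illustration.

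**1. What the exclusion covers.** It covers expected effects of two treatment classes and of GVHD. It is not limited to mild or non-serious events, and it is worded as applying to the trial as a whole, although IRBMED is the only recipient that 4.8 names.

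**2. Whom it reaches.**
- Section 5.4 plans 23 participants per cancer population per arm, so each stratum has 23 × 2 = 46 of 138.
- Prostate: androgen deprivation is an entry criterion (Study Design, 1.4.1.8), so all 46 are covered: 46/138 = 33%.
- Breast: anti-HER2 and endocrine therapy are permitted, not required (1.4.1.7). The share is not given.
- Transplant: the exclusion names GVHD, not transplant status or maintenance chemotherapy. The share with GVHD is not given.
- Reach is therefore at least 33%, with no tighter upper bound than 100%. The synopsis says "most will still be undergoing long-term treatment", but that refers to treatment in general and cannot be converted into a share on the named therapies.

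**3. Routes for an event classed as expected.**

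| Event | IRB (4.8) | DSMC (4.10) | By-arm table (Section 5) |
|---|---|---|---|
| Non-serious, expected | Excluded | No route stated | None planned |
| Serious, expected | Excluded as worded | Unclear: serious events are discussed, exclusion not repeated | None planned |
| Unexpected, or judged due to research procedures | Outside the exclusion; reported if due to research procedures | Not itemized beyond SAE/UaP | None planned |

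The first row is the gap. The second is an inconsistency between two sections.

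**4. What a by-arm table could show.** Event rates are not in the documents, so the rates here are assumptions. With n = 69 per arm, two-sided 5%, and p̄ the mean of the two rates:

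power = Φ{ [ |p1 − p0| − 1.96·√(2p̄(1 − p̄)/n) ] / √[ (p0(1 − p0) + p1(1 − p1))/n ] }

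For 20% v 30%: p̄ = 0.25; 1.96·√(2 × 0.1875/69) = 0.1445; √((0.16 + 0.21)/69) = 0.0732; (0.10 − 0.1445)/0.0732 = −0.61; power 0.27. The same formula gives 0.73 for 20% v 40%, 0.23 for 30% v 40% and 0.67 for 30% v 50%. These use the full sample; a six-monthly report during accrual would hold fewer participants. The table should therefore be descriptive and not a formal test.

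**The case against.** The strongest reply is that the plan has other safeguards, and several of them stand.

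- **A separate DSMC route exists.** A reader might infer that events attributed to these treatments can never reach the safety committee. The documents do not support that. Section 4.8 names only IRBMED, and 4.10 sets up its own six-monthly report under an institutional plan that is not among the documents. Whether the exclusion limits that report is unknown.
- **The sentence covers expected effects only.** Unexpected events fall outside it, whatever their presumed cause.
- **Glasses injuries are already covered.** The Study Design section (1.5.8) warns against wearing the glasses when driving or "when doing motor activity that risks injury with vision impairment". An injury judged to result from study glasses comes from research procedures and is reportable under 4.8. It is not part of this gap.
- **Some outcomes are compared by arm whatever the cause.** Section 5.14.2 compares health care use; 5.13 compares sleep disturbance, anxiety, depression, physical function and global health; 5.14.1 compares sleep measures from the wearable. An excess of harm in these domains could still show. They are not adverse event records, however. They would miss an event that led to no visit and did not move a score, and no path to the DSMC during the trial is stated for them.
- **Section 5.10 can be read as defining coverage, not pooling.** That is fair: it does not forbid a summary by arm. Nor does it require one, and toxicities are only among the items that may be examined.

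It can also be said that this is a 12-week behavioral intervention described as minimal risk. That limits the weight of the point, but the remedy is correspondingly small.

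**Conclusion.** The point holds in a limited form. A written rule excludes expected background-treatment effects from reporting with no severity limit or event list, attribution is unblinded, and no by-arm adverse event table is planned. As a result, an excess of non-serious events of this kind in the SYNC arm has no stated tabulation and no stated route to the DSMC. For serious expected events the finding is an unresolved inconsistency between 4.8 and 4.10, not a demonstrated loss.

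The certain reach is one third of the sample (46 of 138). A reader might take the rule to cover nearly everyone, since all three populations are touched by its wording, but the shares on the named therapies or with GVHD are not given outside the prostate stratum. The size of any missed excess cannot be estimated from the documents.

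The conclusion assumes that the institutional monitoring plan does not already require by-arm listing of these events. If it does, a cross-reference would settle the matter. The primary fatigue comparison is not affected. The change should be made, but the trial's main inference does not depend on it.

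**What to change.** 1. **Section 4.8:** limit the exclusion to individual reports to the IRB. Add, for example: *Adverse events and toxicities noted by coordinators or in the health record during the 12 weeks will be listed for both arms regardless of presumed cause, including those attributed to anti-hormonal therapy, anti-HER2 therapy or GVHD, and tabulated descriptively by arm in each DSMC report and in the final report.*
2. **Section 4.10:** say that the DSMC report contains this table, and state explicitly how serious events classed as expected are handled, so that it agrees with 4.8.
3. **Section 5.10:** summarize toxicities by arm.

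The cost is a short log, one table and three edits. Coordinators already follow up participants over missing surveys (Study Design, 1.5.5), and the health record is already used for utilization (3.3.2). A descriptive safety table is not an efficacy or futility look, so it does not conflict with 5.9.

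There are two downsides. More background events will be listed, which adds noise. Events will also be noted without scheduled questioning by staff who know the arm, so counts could differ between arms through ascertainment alone. The report should say so and present the table without a significance test.
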